7.2 Study period (whole study)

October 30, 2015 to June 30, 2016 (scheduled date of the conclusion of the first study agreement to the date of the last visit of the last subject)

7.3 Endpoints

7.3.1 Primary Efficacy Variable

Change in SBM* frequency from screening period Week 2 to treatment period Week 1

*: Defection without laxatives/enema or digital evacuation. Defection within 24 hours after the use of a laxative or rescue medication will not be deemed as SBM in this study.

[Rationales for the selection]

Weekly bowel movement frequency was set as the efficacy endpoint because weekly bowel movement frequency is specified in the criteria for functional constipation in ROME III. Since it was considered inappropriate to include defecation induced by the use of a rescue medication in efficacy evaluation, SBM frequency was set. Because AJG533 was expected to quickly exert its effect, it was considered appropriate to specify the change in SBM frequency from screening period Week 2 to Week 1 after the start of the study treatment as the primary efficacy endpoint.

The change in SBM frequency from the screening period to Week 1 of the treatment period was also used as the primary endpoint in the clinical study of the approved and marketed drug, Lubiprostone 24 μg .

7.3.2 Secondary efficacy endpoints

- Change in SBM frequency from of the screening period to Week 2 of the treatment period
- Change in SBM frequency from the screening period to the treatment period
- Changes in CSBM* frequency from screening period Week 2 to treatment period Weeks 1 and 2
 - *: SBM without sensation of incomplete evacuation
- Change in CSBM frequency from the screening period to the study drug treatment period
- Proportion of patients who experienced SBM within 24 hours/48 hours after the start of the study treatment
- SBM and CSBM responser ** rates at treatment period Weeks 1 and 2
- **: A responder will be defined as a patient with weekly SBM or CSBM frequency of ≥ 3 and weekly SBM or CSBM frequency improved by ≥ 1 from Screening Period Week 2.
 - Time to the first SBM
 - Use of rescue medication

- · Stool consistency as measured by Bristol Stool Form Scale
- Evaluation of weekly-based severity of constipation for treatment period Week 1 and Week 2

[Rationales for the selection]

This is a generally accepted endpoint used for recently developed constipation drugs and evaluated in the Phase II clinical study in patients with chronic constipation (AJG533/ET1).

7.3.3 Safety endpoints

- TEAEs
- Laboratory test parameters
- · Vital signs

7.4 Method for allocation (randomization) of patients to treatment groups

Each subject confirmed eligible for the study will be assigned to an appropriate treatment group according to the allocation table prepared by the permuted block method.

7.5 Blinding Method

Blinding will be made using the study drug and comparator indistinguishable from it.

7.6 Maintenance of blinding

7.6.1 Method for maintaining blinding

- (1) The study drug allocation manager will confirm that the study drug and comparator (placebo tablet) are indistinguishable from each other in appearance, weight, and package, and then blind the study drug according to the Inventory File and study drug allocation procedure.
- (2) The study drug allocation manager, subject enrollment manager, and sponsor will take appropriate measures to ensure that the study treatment will be blinded for all those involved until key code breaking.
- (3) At the key code breaking, the subject enrollment manager will confirm that Allocation Table and Inventory File provided by the study drug allocation manager are sealed, and that the study treatment is blinded throughout the study period. The subject enrollment manager will also check the cases of emergency unblinding with the EDC system, thereby confirming that blinding is maintained throughout the study period.

7.6.2 Preparation and storage of Inventory File and Allocation Table

The study drug allocation manager will provide the subject enrollment manager with the Inventory File immediately after the study treatment is blinded. The subject enrollment manager will prepare the Allocation Table. The subject enrollment manager will import the Inventory File and Allocation Table to the EDC system, seal them, and strictly store them until key code breaking. Emergency unblinding will be performed using appropriate EDC system functions. It is prohibited to unblind the study treatment without following the predetermined procedure (see "11.3 Emergency unblinding procedure").

7.6.3 Reporting of LDL-cholesterol and HDL-cholesterol measurements

The measurements of LDL-cholesterol and HDL-cholesterol after the start of the study drug treatment (at Visit 7 or discontinuation) will be disclosed to those involved in the study including the investigator, subinvestigator, and sponsor after key code breaking.

In addition, the measurements of LDL-cholesterol or HDL-cholesterol will be prohibited in tests except for this study during the period from enrollment to Visit 7 or until discontinuation except for medically compelling cases.

[Rationales for the selection]

AJG533 treatment may decrease LDL-cholesterol. Because comparing the change in LDL-cholesterol before and after the study drug treatment between subjects might unblind the study treatment, the disclosure of the measurements of LDL-cholesterol and HDL-cholesterol after the start of the study drug (at Visit 7 or discontinuation) was restricted until key code breaking and the measurement of LDL-cholesterol and HDL-cholesterol not specified in the protocol was prohibited after enrollment.

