Pharmacokinetic results showed that the exposure to the drug was dose-dependently increased in the dose range of 2.5 to 20 mg, and that the intake of breakfast reduced the exposure to about 20 to 30%. No accumulation was observed when the drug was repeatedly administered at 2.5, 10, or 20 mg, while accumulation was observed at 5 or 15 mg: it seemed that steady state was reached on Day 8 after the start of treatment at 15 mg.

Pharmacodynamic results showed reduced serum LDL-cholesterol concentration and increased plasma C4 concentration. No specific tendency was noted for serum HDL-cholesterol concentration. Exploratory efficacy examination showed that the change in SBM frequency was increased at 2.5 mg or higher, and that most of the subjects experienced SBM within 24 hours after treatment. The incidence of TEAEs did not increase dose dependently. Although the incidence of diarrhoea was high after the repeated administration at 20 mg, it was determined that AJG533 was tolerated up to 20 mg because all the TEAEs were mild in severity.

(2) Japanese Phase II study (AJG533/ET1)

The Japanese Phase II study was performed in patients with chronic constipation by Ajinomoto Pharmaceuticals.

AJG533 at 5, 10 or 15 mg or placebo was orally administered once daily in 163 patients to examine efficacy and safety.

For efficacy, the primary endpoint, or the change in SBM frequency from screening period Week 2 to treatment period Week 1 (FAS), was significantly increased in the 10 and 15 mg groups as compared to the placebo group. Significant improvement was also observed in the 10 mg and 15 mg groups as compared to the placebo group for many of the other efficacy endpoints set as secondary endpoint. These results suggest the efficacy of AJG533 in patients with chronic constipation. In the 5 mg group, significant improvement as compared to the placebo group was demonstrated for only a few endpoints, although many of the endpoints tended to improve. Based on these efficacy results, AJG533 at 10 and 15 mg once daily was anticipated to show adequate efficacy. The effect of the drug at 5 mg was considered to be inferior to that at 10 or 15 mg.

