None of the treated groups showed any difference in the incidence of TEAEs from the placebo group. Most of observed TEAEs were mild and no death, serious adverse event, adverse event leading to treatment discontinuation, or severe adverse event was observed.

The plasma concentration of A3309 detected in the 1 to 10 mg groups was in the order of picomole and increased dose proportionally. The plasma concentration reached C_{max} within 4 hours after administration and then lowered to a level below the detection limit at 24 hours after administration in the 10-mg group. It was suggested that SBM and complete SBM frequencies were increased and stool consistency improved in the 10-mg group, and that the transit time in the large intestine was shortened (gastrointestinal propulsion was improved) in the 3-mg and 10-mg groups. Total cholesterol and LDL-cholesterol significantly and dose-dependently decreased and C4 dose dependently increased.

(3) Foreign late Phase II study (A3309-002)

The late Phase II study was performed in patients with chronic idiopathic constipation in the United States by Albireo. A3309 at 5, 10, or 15 mg or placebo was administered once daily for 56 days in 190 patients in a double-blind manner to examine the efficacy and safety of A3309.

The change in the weekly SBM frequency from the screening period to Week 1 or to Weeks 1 to 8 was significantly improved in the 10 or 15 mg group as compared to the placebo group. That in the weekly CSBM frequency was significantly improved in the 5, 10, or 15 mg group as compared to the placebo group. The time until the first SBM was significantly reduced and the proportion of subjects with SBM within 24 hours and overall therapeutic effect on stool hardness (improvement) were significantly increased in the 10 or 15 mg group as compared to the placebo group.

The C4 value was significantly increased in the 5, 10, or 15 mg group as compared to the placebo group. Cholesterol and LDL-cholesterol were significantly reduced in the 10 or 15 mg group as compared to the placebo group.

Although TEAEs were generally observed in the active drug and placebo groups, many of them were mild and no serious adverse drug reaction occurred. Many of TEAEs were classified into mild to moderate gastrointestinal disorders. Although they tended to increase dose dependently, they were resolved promptly.

(4) Foreign Phase II study (A3309-003)

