	Contents				
Subject background	Gender, birth date, race, medical history (including surgical history)*1, complications*2, and presence or absence of constipation-predominant IBS				
Observation/investigation items	Study drug compliance, use of concomitant medications, subjective symptoms, objective findings, and study completion				
Vital signs	Height, body weight, blood pressure (systolic and diastolic blood pressures), and pulse rate				
Hematology	White blood cell count, red blood cell count, hemoglobin content, hematocrit, and platelet count				
Blood biochemistry	Total protein, albumin, AST (GOT), ALT (GPT), γ-GTP, ALP, LDH, LAP, total bilirubin, urea nitrogen, creatinine, uric acid, LDL-cholesterol*3, HDL-cholesterol*3, total cholesterol, triglyceride, CRP, CK (CPK), Na, K, Cl, and Ca				
Urinalysis (qualitative)	Glucose, protein, urobilinogen and occult blood				
Items related to bowel movements	Bowel movement status (date and time, stool consistency as measured by Bristol Stool Form Scale, and sensation of complete evacuation), constipation severity assessment (date of assessment and severity assessment), and use of the rescue medication				

^{*1:} Medical history: Medically important symptoms or diseases (e.g., those related to the exclusion criteria) that developed within 5 years and cured before the start of the study treatment All laparotomy histories will be recorded.

^{*2:} Complications: Diseases present or symptoms or signs observed at the start of the study treatment and considered as clinically important

^{*3:} LDL-cholesterol and HDL-cholesterol at Visit 7 and at discontinuation will be investigated in a blinded manner.

Table 10-2 Investigation items and schedule

	-				_ Study	per	iod				
		Screening period									
	Informed consent	Eligibility test (1)	Confirmatio n of laboratory test eligibility assessmen	Eligibility test (2) *2	Day of provisional enrollment		Day of enrollment	Starting day of study treatment	Week 1 Visit day		Week 2 Visit day /at disconti- nuation
visit	1	2		3	4		5		6		7
Test/observation time points (day)				to -23	to -16		-1	1	8	14	15
Informed consent	0										
Enrollment and confirmation of eligibility assessment results "			0		0		0				
Medical history ³ , complications ⁴ , presence or absence of constipation-predominant IBS							0				
Clinical examination		0		0	0		0		0		0
TEAEs								- 			\rightarrow
Subject background (gender, birth date, inpatient/outpatient status, and race)		0									

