10.8 Safety investigation items

(1) Laboratory tests

The following measurements will be performed at SRL, Inc.

Hematology: White blood cell count, red blood cell count, hemoglobin content, hematocrit, and

platelet count

Blood biochemistry: Total protein, albumin, AST (GOT), ALT (GPT), γ-GTP, ALP, LDH, LAP, total

bilirubin, urea nitrogen, creatinine, uric acid, LDL-cholesterol, HDL-cholesterol,

total cholesterol, triglyceride, CRP, CK (CPK), Na, K, Cl, and Ca

Urinalysis (qualitative): Glucose, protein, urobilinogen and occult blood

Samples will be collected by SRL Medisearch Inc. or SRL, Inc. and sent to SRL, Inc. Samples will be refrigerated before collection. Measured samples will be stored at SRL Medisearch Inc. until case fixation. Measurement results will be provided as electronic data to the study site and sponsor and sent as test slips from SRL Medisearch to the study site by mail. However, the measurement results of LDL-cholesterol and HDL-cholesterol after the start of the study treatment (at Visit 7 or at discontinuation) will be disclosed to the persons involved in the study including the investigator, subinvestigator, and sponsor after key code breaking.

(i) Hematology

White blood cell count, red blood cell count, hemoglobin content, hematocrit, and platelet count [Investigation time points: Visits 2, 5, and 7 (or at discontinuation)]

Two mL of whole blood will be drawn in a separately distributed EDTA-2K blood collection tube. Subject ID code and date of blood collection will be documented on its label. The sample will be refrigerated until collection.

(ii) Blood biochemistry (i)

Total protein, albumin, AST (GOT), ALT (GPT), γ -GTP, ALP, LDH, LAP, total bilirubin , urea nitrogen, creatinine, uric acid, total cholesterol, triglyceride, CRP, CK (CPK), Na, K, Cl and Ca [Investigation time points: Visits 2, 5, and 7 (or at discontinuation)]

Blood collection for blood biochemistry (i) and (ii) will be performed using one serum separator blood collection tube and processed as follows:

Five mL of whole blood will be drawn in a separately distributed serum separator blood collection tube.

Separated serum will be dispensed in a designated container, and subject ID code and date of blood collection

43

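### Post-treatment LDL-C and HDL-C are masked to protect the blind, but total cholesterol from the same sample is released, so a route to partial unblinding remains

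*Protocol*

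**What the plan says.** Protocol section 7.6.3 keeps LDL-C and HDL-C taken after the start of treatment (Visit 7 or discontinuation) from the investigator, subinvestigator and sponsor until the key code is broken. The stated reason is: "Because comparing the change in LDL-cholesterol before and after the study drug treatment between subjects might unblind the study treatment". The section also bans LDL-C and HDL-C tests outside the study from enrollment to Visit 7 or discontinuation, except where medically compelling. The footnote to Table 10-1b has the same scope: "LDL-cholesterol and HDL-cholesterol at Visit 7 and at discontinuation will be investigated in a blinded manner".

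Section 10.8 (1) splits the chemistry into two panels drawn in one serum tube. Panel (ii) holds LDL-C and HDL-C. Panel (i) holds the rest, including "creatinine, uric acid, total cholesterol, triglyceride, CRP, CK (CPK), Na, K, Cl and Ca", at Visits 2, 5 and 7 or discontinuation. On release it says: "Measurement results will be provided as electronic data to the study site and sponsor". The only exception is post-treatment LDL-C and HDL-C.

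On the drug's lipid effects, the Background says of the foreign late Phase I study (A3309-001): "Total cholesterol and LDL-cholesterol significantly and dose-dependently decreased and C4 dose dependently increased". Of the foreign late Phase II study (A3309-002) it says: "Cholesterol and LDL-cholesterol were significantly reduced in the 10 or 15 mg group as compared to the placebo group". Of the Japanese Phase I study it says: "No specific tendency was noted for serum HDL-cholesterol concentration".

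**The concern.** The safeguard in 7.6.3 rests on one argument: the drug moves a lipid, so a before-and-after comparison of that lipid could show who received it. By the protocol's own account, the argument also covers total cholesterol, which is reported both before treatment (Visits 2 and 5) and after it.

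Section 7.6.1 commits the parties to keeping treatment blinded for everyone until key code breaking, and 7.6.4 places that after data fixation. While total cholesterol is visible, two groups still make judgements that ought to be blind:

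- Investigators assess causality and outcome of TEAEs at Visit 7 and during the two-week follow-up.
- The sponsor settles PPS exclusions and data adoption, and re-examines the covariate and subgroup items and categories at the blinded review. It receives results from all subjects, which is the between-subject comparison that 7.6.3 wants to prevent.

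**Working it through.** **Step 1: what is masked and what is released.**

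- *LDL-C and HDL-C:* panel (ii). Visit 2 and 5 values are released; Visit 7 or discontinuation values are withheld; the off-protocol ban applies.
- *Total cholesterol:* panel (i). Visit 2, 5 and 7 or discontinuation values are all released; the ban does not apply.

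Sections 7.6.3 and 10.8, the footnotes to Tables b and 10-1b, and the schedule rows of Tables c and 10-2 name only LDL-C and HDL-C. The general duty in 7.6.1 (2) to take appropriate measures does not mention total cholesterol. Nothing else in the protocol closes the gap.

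**Step 2: does total cholesterol carry a treatment signal?**

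- *A3309-001:* 14 days, five subjects per group (section 11.4). Significant, dose-dependent fall; no separate comparison reported for 10 mg.
- *A3309-002:* 56 days. Significant reduction at 10 and 15 mg against placebo. The text says cholesterol alongside LDL-C, read here as total cholesterol.
- *Japanese Phase I:* LDL-C fell and HDL-C showed no specific tendency; total cholesterol is not mentioned.

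So the direction and the dose are documented. That total cholesterol tracks the LDL-C change after 14 days in this population is an inference. No reported HDL-C movement would offset a fall in LDL-C.

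**Step 3: how much could be guessed?** The protocol states no figure to reproduce. Assume that the change is normal with the same SD in both arms, that allocation is 1:1, and that the arm means differ by k SDs. Each subject is assigned by whether the fall exceeds the midpoint, which the pooled mean approximates under 1:1 allocation. Then P(correct) = Φ(k/2):

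- k = 0.5: Φ(0.25) = 0.599
- k = 1.0: Φ(0.50) = 0.691
- k = 1.5: Φ(0.75) = 0.773

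Chance is 0.50.

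**Step 4: what significance in A3309-002 implies.** Section 11.4 gives denominators of 46 (placebo) and 47 (10 mg). Assuming these apply to the cholesterol comparison, and an unadjusted two-sided 5% t-test, the smallest observed standardised difference that reaches significance is t(0.975; 91) × √(1/46 + 1/47) = 1.986 × 0.207 = 0.41. This corresponds to Φ(0.206) = 0.58 correct. It is a minimum for the observed difference in that study, not an estimate for this trial.

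**Step 5: timing.** Treatment Week 1 is the first 168 hours from the first dose (13.3) and is recorded in the patient diary (10.7). Visit 7 falls on Day 15 to 17 (Table 10-3). A completer's Week 1 data therefore precede the Visit 7 sample.

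**The case against.** A reader might infer that the blind is open, or that site and sponsor can read off each subject's arm. The documents do not support that. Section 7.6.3 says only that unblinding might occur, no effect size is given, and at the values above many subjects would be misclassified. A reader might also infer that the primary result is compromised. For completers the diary entries come before Visit 7, the FAS is defined mechanically (13.2), and the ANCOVA covariate is fixed (13.6.1.1). PPS is a sensitivity analysis, and the blinded review feeds adjusted and subgroup analyses. The one remaining path to the primary analysis is data adoption under separate standards that are not shown.

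A further argument is that the bowel diaries are themselves informative. The Phase II changes in section 7.1.3, 5.66 ± 4.15 at 10 mg and 2.60 ± 2.89 on placebo, differ by 3.06 / √((4.15² + 2.89²)/2) = 3.06 / 3.58 = 0.86 SD. By the same formula that gives Φ(0.43), or about 67% correct. This lowers the priority but does not remove the point: the diary is the endpoint and cannot be hidden, whereas total cholesterol can, and the protocol chose to mask lipids despite the diaries.

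TEAE exposure is also narrower than it first looks. Section 7.1.3 says that most TEAEs in Phase II first appeared early, and in Table 10-5 an event counts as related unless it meets the criteria for not related. What remains is late causality and outcome judgements, and learning across subjects at a site.

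Triglyceride from the same sample is released too, but no drug effect on it is reported. Section 11.4 shows one isolated increase at 10 mg in Phase I. The case rests on total cholesterol.

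**Conclusion.** The point holds at moderate severity. The masking in 7.6.3 is incomplete by its own reasoning: total cholesterol from the same tube is released before key code breaking, and the protocol reports that the drug lowers it together with LDL-C. A route to partial, probabilistic unblinding stays open. Its size is unknown; 60% to 77% correct guesses follow only from assumed shifts of 0.5 to 1.5 SD.

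Significance at 10 mg is documented in one study only, over 56 days against 14 here. The exposure is mainly late TEAE causality and outcome, PPS and data-adoption decisions, and the blinded review. Completers' Week 1 data are largely insulated, so this is not a threat to the primary comparison as such. It cannot be left to a statistical analysis plan, because values already released cannot be masked again.

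**What to change.** Move post-treatment total cholesterol (Visit 7 or discontinuation) into the masked panel, biochemistry (ii), for release only after key code breaking. The text to change is:

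- section 7.6.3;
- section 10.8 (1), including its rationale;
- the footnotes to Tables b and 10-1b;
- the biochemistry rows of Tables c and 10-2.

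Extend the ban on off-protocol testing to total cholesterol, keeping the existing exception for medically compelling cases. Masking triglyceride is optional, since no drug effect on it is reported. Make the change before the first Visit 7 or discontinuation results are released.

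The cost is small: post-treatment serum is already dispensed into two tubes, so the work is a change to the laboratory's reporting set-up plus protocol wording. The downside is that sites see the total cholesterol value later.

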7.6.4 Key code breaking

The subject enrollment manager will break the key code after all electronic case report forms are prepared and data are fixed.

8. Selection and Enrollment of Subjects

The selection of prospective patients to whom the explanation for informed consent is given, acquisition of consent, confirmation of eligibility, and enrollment of subjects (those who provided consent) will be performed in accordance with the following procedures.

